#### **Disease Parameters**

Measurable disease: Measurable lesions are defined as those that can be accurately measured in at least one dimension (longest diameter to be recorded) as  $\geq 20$  mm by chest x-ray or as  $\geq 10$  mm with CT scan, MRI, or calipers by clinical exam. All tumor measurements must be recorded in millimeters (or decimal fractions of centimeters).

Malignant lymph nodes: To be considered pathologically enlarged and measurable, a lymph node must be  $\geq 15$  mm in short axis when assessed by CT scan (CT scan slice thickness recommended to be no greater than 5 mm). At baseline and in follow-up, only the short axis will be measured and followed.

Non-measurable disease: All other lesions (or sites of disease), including small lesions (longest diameter  $< 10$  mm or pathological lymph nodes with  $\geq 10$  to  $< 15$  mm short axis), are considered non-measurable disease. Bone lesions, leptomeningeal disease, ascites, pleural/pericardial effusions, lymphangitis cutis/pulmonitis, inflammatory breast disease, and abdominal masses (not followed by CT or MRI), are considered as non-measurable.

Note: Cystic lesions that meet the criteria for radiographically defined simple cysts should not be considered as malignant lesions (neither measurable nor non-measurable) since they are, by definition, simple cysts.

‘Cystic lesions’ thought to represent cystic metastases can be considered as measurable lesions, if they meet the definition of measurability described above. However, if non-cystic lesions are present in the same patient, these are preferred for selection as target lesions.

Target lesions: All measurable lesions up to a maximum of 2 lesions per organ and 5 lesions in total, representative of all involved organs, should be identified as **target lesions** and recorded and measured at baseline. Target lesions should be selected on the basis of their size (lesions with the longest diameter), be representative of all involved organs, but in addition should be those that lend themselves to reproducible repeated measurements. It may be the case that, on occasion, the largest lesion does not lend itself to reproducible measurement in which circumstance the next largest lesion which can be measured reproducibly should be selected. A sum of the diameters (longest for non-nodal lesions, short axis for nodal lesions) for all target lesions will be calculated and reported as the baseline sum diameters. If lymph nodes are to be included in the sum, then only the short axis is added into the sum. The baseline sum diameters will be used as reference to further characterize any objective tumor regression in the measurable dimension of the disease.

Non-target lesions: All other lesions (or sites of disease) including any measurable lesions over and above the 5 target lesions should be identified as **non-target lesions** and should also be recorded at baseline. Measurements of these lesions are not required, but the presence, absence, or in rare cases unequivocal progression of each should be noted throughout follow-up.

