## 9 MEASUREMENT OF EFFECT

### 9.1 *Antitumor Effect – Solid Tumors*

Each time a tumor assessment occurs, response and progression will be evaluated in this study using both the new international criteria proposed by the revised Response Evaluation Criteria in Solid Tumors (RECIST) guideline (version 1.1) [*Eur J Ca* 45:228-247, 2009] as well as immune-related response criteria (irRC). Changes in the largest diameter (unidimensional measurement) of the tumor lesions and the shortest diameter in the case of malignant lymph nodes are used in the RECIST criteria. Criteria for immune-related response criteria are described later in this section.

Tumor assessments will be performed approximately every 3 months in all treatment arms.

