### New Lesion Measurement

The irRC are tumor assessment criteria that have been developed to better capture the activity of immunotherapeutic agents. These criteria have been used with success in clinical studies that were performed with ipilimumab in advanced metastatic melanoma and in lung cancer.

Additional tumor response data will be collected, beyond what is required to apply the RECIST criteria. More specifically, the investigator will have to record in the CRF the bi-dimensional measurements for each new lesion which has become measurable in each tumor assessment.

To support evaluation of progression-free survival based on irRC criteria (irPFS) in this indication, investigators must perform tumor assessments (including new lesion measurements) during the Toxicity/Progression Follow-up Phase in subjects who have experienced RECIST progression until the total sum of product diameters (SPD including new lesions) has increased 25% or more from the nadir or until subjects discontinue study therapy regardless of whether the subject is initiating subsequent therapy. All available post RECIST progression tumor imaging- based assessments during this phase in the study must be entered into the CRF, including any standard of care assessments and any assessments performed while under non-study subsequent cancer therapy.

Any subject who develops an objective tumor response (CR or PR) or progression (PD) is required to undergo confirmatory scans no less than 4 weeks since the prior scan in order to verify the reliability of the radiologic finding. Sites are encouraged to collect additional CT scans after RECIST PD has been confirmed, as long as a subsequent line of therapy has not been initiated.

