### **Definition of Tumor Response Using irRC**

#### **Calculation of Immune-related Sum of Products of Diameters (irSPD)**

The irSPD incorporates measurable new lesions that may have developed on-study, providing an assessment that includes both index and new lesions. The tumor assessment performed during Screening will serve as the baseline for determination of tumor response using irRC.

irSPD at Baseline: The sum of the product of the diameters for all index lesions identified prior to randomization. At baseline, irSPD and SPD are the same.

irSPD at TA: For every post-randomization TA collected, per protocol Section 5.1 or as clinically indicated including post mWHO PD TA, the irSPD at TA will be calculated using tumor imaging scans. Both index lesions and any measurable new lesions that have developed on study will be included.

irSPD Nadir: For tumors that are assessed more than one time after baseline, the lowest value of the irSPD (irSPD Baseline or irSPD at TA) is used to classify subsequent TAs for each subject. Because ipilimumab treatment may result in complex tumor dynamics in which index lesions may shrink while new lesions appear, the irSPD nadir may be different from the SPD nadir, and may occur either before or after the SPD nadir.

At baseline, the irSPD is measured and recorded.

At each subsequent assessment timepoint, a separate assessment of timepoint overall response will be obtained for that timepoint. The sum of products of perpendicular diameters calculated and recorded at each post-baseline timepoint for immune-related response purposes (irSPD) include measurements of index lesions and also include measurable new lesions which are not too small to measure at this timepoint. A value of 25 mm^2 (5 mm x 5 mm) is imputed for each index and previously measurable new lesion which is present but too small to measure.

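### The irRC measurement instructions contradict each other for lymph nodes and are incomplete for other index lesions

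*Combined protocol and SAP*

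**What the plan says.** Section 9.1 sets up two systems at once: "Each time a tumor assessment occurs, response and progression will be evaluated in this study using both the new international criteria" of RECIST 1.1, together with irRC.

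**Rules written in RECIST terms (Disease Parameters).**
- A measurable lesion is one that "can be accurately measured in at least one dimension (longest diameter to be recorded").
- For malignant nodes: "At baseline and in follow-up, only the short axis will be measured and followed".
- For the baseline total: "A sum of the diameters (longest for non-nodal lesions, short axis for nodal lesions) for all target lesions will be calculated". A separate sentence there says that only a node's short axis enters the sum.

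**Rules written for irRC.**
- New Lesion Measurement announces data beyond RECIST and then specifies that "the investigator will have to record in the CRF the bi-dimensional measurements for each new lesion which has become measurable in each tumor assessment".
- Calculation of irSPD defines the baseline value as "The sum of the product of the diameters for all index lesions identified prior to randomization". After baseline it is a sum of products of perpendicular diameters over index lesions plus measurable new lesions. The value is to be recorded at baseline and at each later timepoint.
- Timepoint Overall Response Using irRC sets irPR at a 50% fall in irSPD from baseline and irPD at a 25% rise over the nadir.

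**Elsewhere.** Section 3.2 has baseline lesions, nodes included, measured under RECIST/irRC criteria. Section 12.3 (Efficacy Analyses) defines primary PFS by RECIST v1.1. It then repeats PFS, response rate, duration of response and duration of stable disease under irRC as additional secondary endpoints.

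**The concern.** A product needs two numbers, and the lesion rules name one. For nodes, the second number is excluded by an unqualified sentence about what is measured, not merely about what is summed. For other lesions present at baseline, no sentence tells the site to enter a perpendicular diameter, and the place where the irRC additions to the CRF are spelled out mentions new lesions only. The protocol also uses *index lesion* for irRC and *target lesion* for RECIST (at most 5, at most 2 per organ) without saying whether they are the same lesions.

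A site that works literally from Disease Parameters and New Lesion Measurement would leave the analyst without irSPD for the lesions that make up the baseline. The analyst would then have to exclude those patients from the irRC analyses or improvise a substitute for the missing diameter. Sites that read the sections differently would also supply data that are not comparable.

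**Working it through.** **1. The plan's own figure.** An index lesion that is present but too small to measure is assigned 25 mm², given as 5 mm x 5 mm. 5 x 5 = 25, so this reproduces, and it confirms that index lesions enter irSPD as a product of two diameters.

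**2. The instructions side by side.**

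| Lesion | Disease Parameters | irSPD definition | Relation |
|---|---|---|---|
| Node present at baseline | Short axis only | Product of perpendicular diameters | Direct contradiction |
| Non-nodal lesion present at baseline | Longest diameter | Product of perpendicular diameters | Second diameter implied, not expressly requested |
| New measurable lesion | – | Product of perpendicular diameters | Consistent: two diameters requested for the CRF |

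The node sentence cannot be read as a summing rule only, because the summing rule is stated separately under target lesions.

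**3. Does one diameter determine the irRC category?** All lesion sizes here are assumptions chosen for illustration. The baseline value is taken as the nadir where a rise is computed. Formula: change = (irSPD now – reference irSPD) / reference irSPD.

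*Stable node 30 x 20 mm, new lesion 12 x 11 mm.*
- irSPD as defined: 600 to 600 + 132 = 732, which is 132/600 = +22.0%, below 25% (irSD).
- Short axis squared: 400 to 532, which is 132/400 = +33.0%, above 25% (irPD).

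*Stable non-nodal lesion 30 x 20 mm, new lesion 14 x 12 mm.*
- irSPD as defined: 600 to 600 + 168 = 768, which is 168/600 = +28.0% (irPD).
- Longest diameter squared: 900 to 1068, which is 168/900 = +18.7% (irSD).

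*Node growing from 20 x 30 to 20 x 40 mm.* irSPD 600 to 800, which is 200/600 = +33.3% (irPD). The short axis shows 0%.

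*Node shrinking from 20 x 40 to 20 x 20 mm.* irSPD 800 to 400, which is –50% and meets the irPR threshold. The short axis again shows 0%.

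**4. Range of true values behind one recorded diameter.**
- Non-nodal lesion, longest diameter 40 mm, stable, new lesion 15 x 15 = 225 mm². If the perpendicular is 0.5 to 1.0 times the longest diameter, the baseline is 800 to 1600 mm² and the true rise runs from 225/800 = 28.1% down to 225/1600 = 14.1%.
- Node, short axis 20 mm, stable, new lesion 12 x 12 = 144 mm². If the long axis is 20 to 40 mm, the baseline is 400 to 800 mm² and the true rise runs from 144/400 = 36% down to 144/800 = 18%.

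Both ranges straddle 25%, so the recorded diameter alone cannot settle whether irPD has occurred.

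**The case against.** The best defense is that Section 9.1 describes two measurement systems and keeps them apart. The sentence that begins "Changes in the largest diameter (unidimensional measurement) of the tumor lesions" ends by assigning those diameters to RECIST, and the next sentence says that the irRC criteria follow later. Section 3.2 calls for irRC measurement before therapy, the study calendars in Section 8 schedule RECIST/irRC evaluations, and irSPD is to be recorded at baseline, when only index lesions exist. Two diameters are therefore required by implication. The new-lesion instruction sits under a heading about new lesions and does not claim to list every irRC data item. The CRF is not among the documents, so a missing field is an inference.

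Most of this stands, and it rules out three stronger readings.

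- A reader might infer that two diameters are wanted only on new lesions. That is true of the explicit CRF instruction, not of the protocol as a whole.
- A reader might infer that irSPD cannot be computed, or that every patient with a nodal index lesion is misclassified. A site that follows the irSPD text has the data, stored scans can be re-read, and the protocol gives no proportion of patients with nodal index lesions.
- A reader might take the squared-diameter results as what the plan would produce. No section proposes squaring. Those cases show only what an improvised workaround would do.

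What the defense does not answer is the node sentence. It is unqualified, it concerns measurement, and nothing exempts irRC from it. An implication drawn from other sections does not override an explicit *only*. Nor does the defense supply the missing link between index and target lesions.

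**Conclusion.** The instructions conflict for nodes and are incomplete for non-nodal index lesions. A site that follows Disease Parameters and New Lesion Measurement as written would lack the data for irSPD, and the 25% and 50% categories cannot be recovered from one diameter. How many patients would be affected cannot be estimated from the documents. The examples rest on assumed lesion sizes and show only that the category can change, in either direction.

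The reach is limited to PFS, response rate, duration of response and duration of stable disease under irRC. These are secondary, and the Multiplicity Issues text applies no formal testing to them. A reader might extend the point to the primary endpoint, because Section 9.1 sends some suspected progressions to irRC before they count. Section 12.3, however, defines primary progression by RECIST v1.1, which needs only the single diameters, so the primary analysis as defined there is not affected. The sample size is not affected either.

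The irRC text also carries traces of another source. It refers to assessments after mWHO progression, a system not otherwise used here, and to Section 5.1 for assessments, which in this protocol describes the dorgenmeltucel-L product. These do not alter the irSPD formula, but they suggest that the text was not fully matched to the RECIST rules around it.

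**What to change.** In Section 9.1:

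1. Limit the short-axis-only sentence for nodes to the RECIST sum. It need not be deleted, since RECIST relies on it.
2. State under target lesions and under New Lesion Measurement that the longest diameter and its perpendicular are both recorded in the CRF for every index lesion, nodes included, at baseline and at every assessment. RECIST then uses the longest diameter (short axis for nodes), and irRC uses the product.
3. Define the irRC index lesions as the RECIST target lesions.
4. Remove the mWHO reference, and correct the Section 5.1 cross-reference in the same edit.
5. Check that the CRF has a field for the second diameter, and add one if it does not.

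The cost is one extra diameter per target lesion, taken from the same scan or examination. For patients already enrolled, the second diameter can be re-read from stored scans where it was not recorded. Skin lesions measured only by calipers may not be recoverable, because photography with a ruler is recommended and not required. That is a reason to make the change early.

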### **Methods for Evaluation of Measurable Disease**

All measurements should be taken and recorded in metric notation using a ruler or calipers. All baseline evaluations should be performed as closely as possible to the beginning of treatment and never more than 4 weeks before the beginning of the treatment.

The same method of assessment and the same technique should be used to characterize each identified and reported lesion at baseline and during follow-up. Imaging-based evaluation is preferred to evaluation by clinical examination unless the lesion(s) being followed cannot be imaged but are assessable by clinical exam.

Clinical lesions: Clinical lesions will only be considered measurable when they are superficial (*e.g.*, skin nodules and palpable lymph nodes) and  $\geq 10$  mm diameter as assessed using calipers (*e.g.*, skin nodules). In the case of skin lesions, documentation by color photography, including a ruler to estimate the size of the lesion, is recommended.

Chest x-ray: Lesions on chest x-ray are acceptable as measurable lesions when they are clearly defined and surrounded by aerated lung. However, CT is preferable.

Conventional CT and MRI: This guideline has defined measurability of lesions on CT scan based on the assumption that CT slice thickness is 5 mm or less. If CT scans have slice thickness greater than 5 mm, the minimum size for a measurable lesion should be twice the slice thickness. MRI is also acceptable in certain situations (*e.g.* for body scans).

Use of MRI remains a complex issue. MRI has excellent contrast, spatial, and temporal resolution; however, there are many image acquisition variables involved in MRI, which greatly impact image quality, lesion conspicuity, and measurement. Furthermore, the availability of MRI varies globally. As with CT, if an MRI is performed, the technical specifications of the scanning sequences used should be optimized for the evaluation of the type and site of disease. Furthermore, as with CT, the modality used at follow-up should be the same as was used at baseline and the lesions should be measured/assessed on the same pulse sequence. It is beyond the scope of the RECIST guidelines to prescribe specific MRI pulse sequence parameters for all scanners, body parts, and diseases. Ideally, the same type of scanner should be used and the image acquisition protocol should be followed as closely as possible to prior scans. Body scans should be performed with breath-hold scanning techniques, if possible.

PET-CT: At present, the low dose or attenuation correction CT portion of a combined PET-CT is not always of optimal diagnostic CT quality for use with RECIST measurements. However, if the site can document that the CT performed as part of a PET-CT is of identical diagnostic quality to a diagnostic CT (with IV and oral contrast), then the CT portion of the PET-CT can be used for RECIST measurements and can be used interchangeably with conventional CT in accurately measuring cancer lesions over time. Note, however, that the PET portion of the CT introduces additional data which may bias an investigator if it is not routinely or serially performed.

Ultrasound: Ultrasound is not useful in assessment of lesion size and should not be used as a method of measurement. Ultrasound examinations cannot be reproduced in their entirety for independent review at a later date and, because they are operator dependent, it cannot be guaranteed that the same technique and measurements will be taken from one assessment to the next. If new lesions are identified by ultrasound in the course of the study, confirmation by CT or MRI is advised. If there is concern about radiation exposure at CT, MRI may be used instead of CT in selected instances.

Endoscopy, Laparoscopy: The utilization of these techniques for objective tumor evaluation is not advised. However, such techniques may be useful to confirm complete pathological response when biopsies are obtained or to determine relapse in trials where recurrence following complete response (CR) or surgical resection is an endpoint.

Tumor markers: Tumor markers alone cannot be used to assess response. If markers are initially above the upper normal limit, they must normalize for a patient to be considered in complete clinical response. Specific guidelines for both CA-125 response (in recurrent ovarian cancer) and PSA response (in recurrent prostate cancer) have been published [*JNCI* 96:487-488, 2004; *J Clin Oncol* 17, 3461-3467, 1999; *J Clin Oncol* 26:1148-1159, 2008]. In addition, the Gynecologic Cancer Intergroup has developed CA-125 progression criteria which are to be integrated with objective tumor assessment for use in first-line trials in ovarian cancer [*JNCI* 92:1534-1535, 2000].

Cytology, Histology: These techniques can be used to differentiate between partial responses (PR) and complete responses (CR) in rare cases (*e.g.*, residual lesions in tumor types, such as germ cell tumors, where known residual benign tumors can remain).

The cytological confirmation of the neoplastic origin of any effusion that appears or worsens during treatment when the measurable tumor has met criteria for response or stable disease is

mandatory to differentiate between response or stable disease (an effusion may be a side effect of the treatment) and progressive disease.

**FDG-PET:** While FDG-PET response assessments need additional study, it is sometimes reasonable to incorporate the use of FDG-PET scanning to complement CT scanning in assessment of progression (particularly possible 'new' disease). New lesions on the basis of FDG-PET imaging can be identified according to the following algorithm:

- a. Negative FDG-PET at baseline, with a positive FDG-PET at follow-up is a sign of PD based on a new lesion.
- b. No FDG-PET at baseline and a positive FDG-PET at follow-up: If the positive FDG-PET at follow-up corresponds to a new site of disease confirmed by CT, this is PD. If the positive FDG-PET at follow-up is not confirmed as a new site of disease on CT, additional follow-up CT scans are needed to determine if there is truly progression occurring at that site (if so, the date of PD will be the date of the initial abnormal FDG-PET scan). If the positive FDG-PET at follow-up corresponds to a pre-existing site of disease on CT that is not progressing on the basis of the anatomic images, this is not PD.
- c. FDG-PET may be used to upgrade a response to a CR in a manner similar to a biopsy in cases where a residual radiographic abnormality is thought to represent fibrosis or scarring. The use of FDG-PET in this circumstance should be prospectively described in the protocol and supported by disease-specific medical literature for the indication. However, it must be acknowledged that both approaches may lead to false positive CR due to limitations of FDG-PET and biopsy resolution/sensitivity.

Note: A 'positive' FDG-PET scan lesion means one which is FDG avid with an uptake greater than twice that of the surrounding tissue on the attenuation corrected image.

